8. STATISTICS AND DATA ANALYSIS	20-23
9. DATA MANAGEMENT	23-24
10. ETHICAL AND REGULATORY CONSIDERATIONS	24-26
11. DISSEMINATION POLICY	26-27
12. SAFETY REPORTING	27
13. FINANCE AND INSURANCE	28
FLOW DIAGRAM OF PATIENT PARTICIPANTS THROUGH STUDY	29
FLOW DIAGRAM OF THERAPIST PARTICIPANTS THROUGH STUDY	30
REFERENCES	31-33

ii. List of Key Abbreviations

SVV: Subjective Visual Vertical

SCP: Scale for Contraversive Pushing

MRS: Modified Rankin Scale

NIHSS: National Institute for Health Stroke Scale

DC: Discharge

iii. Trial Summary

Study Title: Identifying vertical perception loss in people with acute stroke: A feasibility study.

Short Title: Feasibility of measuring vertical perception in acute stroke

Study Design: Cross sectional, feasibility study

Study Participants: Acute stroke patients in inpatient care

Planned Sample Size: As this is a feasibility study no planned sample size but up to 250 people could be screened for participation

Length of Participant Involvement: Equal to length of stay on the stroke unit

Planned Study Period: 01/03/24 – 31/8/24

Primary Objective: To establish the feasibility of completing the Catherine Bergego Scale, Scale for Contraversive Pushing (SCP) and bucket test in a clinical environment with acute stroke patients to assist with identification of vertical perception loss

Primary Outcome Measure:

The primary outcome is to understand the feasibility of completing the suite of outcome measures in an acute stroke setting:

- Proportion (%) of patients on whom the assessments are attempted.
- Percentage of patients who are able to complete all three assessments within four weeks of admission.
- Time taken to complete the three measures in an acute clinical setting
- A recommendation regarding the most feasible time point to complete these assessments.

Secondary Objectives:

To gain a further understanding of vertical perception loss in acute stroke patients.

Secondary Outcome Measures:

- An understanding of factors that prevent or facilitate completion of these three assessments
- An understanding of healthcare professionals' experiences of completing these assessments in an acute stroke unit.

- An understanding of whether people with stroke (or their advocates) find it appropriate to complete all three assessments in an acute stroke setting.
- Percentage of patients admitted to an acute stroke unit showing a positive test for vertical perception loss within four weeks of admission.

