It is known that some people with stroke present with loss of vertical perception (Dai et al., 2021b, Utz et al., 2011, Perennou et al., 2008, Karnath et al., 2000). It has been established that loss of vertical perception is related to an inability to actively align the body with respect to gravity following stroke (Dai et al., 2022). It is measured using subjective visual vertical (SVV) (Perennou et al., 2008), subjective haptic vertical (SHV) (Utz et al., 2011) or subjective postural vertical (SPV) (Karnath et al., 2000). Furthermore, it has been associated with neglect (a disorder of spatial awareness whereby people with stroke fail to attend to their contralesional space/body) (Gammeri et al., 2020, Utz et al., 2011, Funk et al., 2010), and pushing behaviour (in which the patient uses their nonparetic extremities to push themselves to their paretic side leading to a loss of balance) (Bergmann et al., 2016, Karnath and Broetz, 2003). There is much debate about the terminology used to describe pushing behaviour (Nolan et al., 2022, Dai and Pérennou, 2021). This debate has led to a lack of a consistent approach to research, measurement tools and effective interventions to address this problem (Dai and Pérennou, 2021). A recent recommendation has been made that lateropulsion should be used to describe all those people that present with a tilted posture following stroke (Nolan et al., 2022, Dai and Pérennou, 2021). It could be argued that lateropulsion describes a wider range of those with stroke who are unable to align to vertical whereas pushing describes those at the more severe end of this spectrum. This argument is compounded by the different scales and cut off points used to identify pushing in research studies (Paci et al., 2023). Recently, the magnitude of visual vertical loss has been found to be related to that of lateropulsion (Dai et al., 2021b). It has been established that people with stroke that present with neglect or lateropulsion require longer periods of rehabilitation and have a worse functional outcome (Nolan et al., 2021, Babyar et al., 2015, Funk et al., 2011). Lateropulsion has been identified as the primary factor in disordered gait and balance after stroke (Dai et al., 2021a). This contributes to greater disability for the individual, safety concerns during rehabilitation and in the community, increases the burden on family and caregivers (Gomes-Osman and Kloos, 2021) and contributes to an estimated societal cost of £26 billion per year in the UK (Patel et al., 2019).

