To establish the feasibility of completing the Catherine Bergego Scale (neglect) (Azouvi et al., 1996), Scale for Contraversive Pushing (SCP) (Karnath et al., 2002) and bucket test (SVV) (Zwergal et al., 2009) in a clinical environment with acute stroke patients to assist with identification of vertical perception loss.

The secondary research questions that this study will aim to address are:

- What percentage of patients admitted to an acute stroke unit show a positive test for vertical perception loss within four weeks of admission (evidence of subjective visual vertical (SVV) tilt on either bucket test or Catherine Bergego Scale or evidence of subjective postural vertical (SPV) tilt on SCP)
- For those able to complete the assessments, does vertical perception loss show any relationship with:
 - Discharge (DC) destination
 - Care package size on discharge
 - Number of inpatient falls
 - Level of functional independence on discharge
- Is there a trend for any element of the SCP or the Catherine Bergego to be more correlated with SVV tilt.

2. Objectives and outcome measures.

Primary objective:

To establish the feasibility of completing the Catherine Bergego Scale, the Scale for Contraversive Pushing (SCP) and the bucket test in a clinical environment with acute stroke patients, to assist with identification of vertical perception loss.

Primary outcomes:

The primary outcome is to understand the feasibility of completing the suite of outcome measures in an acute stroke setting:

- Proportion (%) of patients on whom the assessments are attempted.
- Percentage of patients who are able to complete all three assessments within four weeks of admission.
- Time taken to complete the three measures in an acute clinical setting
- A recommendation regarding the most feasible time point to complete these assessments.

Secondary outputs:

The secondary aims are to gain a further understanding of vertical perception loss in acute stroke patients.

- An understanding of factors that prevent or facilitate completion of these three assessments
- An understanding of healthcare professionals' experiences of completing these assessments in an acute stroke unit.
- An understanding of whether people with stroke (or their advocates) find it appropriate to complete all three assessments in an acute stroke setting.
- Percentage of patients admitted to an acute stroke unit showing a positive test for vertical perception loss within four weeks of admission.

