- To explore the relationship between vertical perception loss and:
 - Discharge destination
 - Care package size on discharge
 - Number of inpatient falls
 - Level of functional independence on discharge
- To explore if any elements of the Catherine Bergego Scale or Scale for Contraversive Pushing show a trend for a relationship to vertical perception loss

3. Trial Design

This is a mixed methods feasibility study with data collected using a cross sectional design, focus groups and surveys. As the nature of acceptability is subjective a qualitative element utilising a phenomenological approach (Nicholls, 2009) will be nested into the study. This will allow an exploration of the experiences of professionals in completing or undertaking the outcome measures via focus groups. People with stroke (or their advocates) acceptability will be explored using a survey, a pragmatic approach to reduce the burden on research participants. Hence, a convergent mixed methods approach will be used (Creswell and Creswell, 2018) to fully answer the research aim and questions.

4. Trial Setting

The population to be studied will be acute stroke patients admitted to a stroke unit. A non-probability, convenience sample will be used. All patients with a diagnosis of stroke admitted for 72 hours to a single stroke unit at Royal Hampshire County Hospital will be considered in the present study.

Calculation of the sample size for a feasibility study is challenging (Hooper, Unknown). Sample sizes of between 24 and 50 participants have been recommended to allow calculation of a sample size for

a full-scale study (Sim and Lewis, 2012, Lancaster et al., 2004, Browne, 1995). Therefore a pragmatic approach to calculating the sample size will be taken. All those admitted to the stroke unit over a six-month period will be eligible for inclusion, meaning approximately 250 people will be screened for participation.

5. Participant Eligibility Criteria

Inclusion and exclusion criteria:

INCLUSION	EXCLUSION
Diagnosis of first stroke by stroke consultant based on clinical or radiographical findings	Under the age of 18
Admitted to stroke unit with a length of stay of over 72 hours	Diagnosis of Transient Ischaemic Attack (TIA)
Ability to consent or an advocate to consent on their behalf	Previous diagnosis of stroke or other neurological diagnosis affecting the brain with residual impairment
Pre-morbid Modified Rankin Scale of less than 4	Patients on an end of life pathway

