	Patients with pre-morbid visual impairment that will not allow them to see the bucket test. Glasses can be worn.
	Inability to speak the English language and no interpreter can be found

6. Trial Procedures

Recruitment

All patients admitted to an acute stroke unit, who meet the inclusion criteria, may be invited to participate. Potential participants will be identified during the daily handover by members of the clinical or research team. Those meeting the inclusion criteria will be approached by a member of the research or clinical team and invited to participate. This will take place between 48 hours and one week after admission. Potential participants will be provided with the participant information sheet (PIS) regarding this study. If the patient is unable to consent due to cognitive or language impairment or low level of consciousness then their advocate will be approached. Where possible potential participants will be supported to consent using information in different formats (e.g.

through use of pictures) or the skill of appropriate members of the clinical team (e.g. speech and language therapists).

The number of people admitted to hospital with stroke who have language or cognitive impairments that may prevent them being able to consent is substantial. To exclude these potential participants would significantly impact the validity and generalisability of the results. Especially as those with significant strokes are more likely to present with vertical perception loss as well as cognitive and language impairment. If they were excluded a large number of patients with vertical perception loss may not be identified. These groups are often underrepresented in stroke research. If someone is unable to consent an advocate will be approached to consent on their behalf.

Those taking consent will decide on capacity. This includes the chief investigator and the stroke research nurse. Both have significant experience working with people with stroke. Both have undergone Good Clinical Practice training and Mental Capacity Act Training. If in any doubt about capacity other members of the healthcare team (e.g., Speech and Language Therapists) can give advice as to whether the potential participant has capacity or whether their advocate should be approached.

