For people with stroke or their advocates, acceptability of the measures will be assessed throughout. Alongside their ability to complete the outcome measures, their willingness to complete them will be documented. At the point they complete all the outcome measures (or at 4 weeks if they are unable to complete the measures) participants (or their advocates) will be asked, by the therapist completing their measures or a member of the research team, to complete a short survey asking about the acceptability of the outcome measures. The questions will be based on the theoretical framework of acceptability (Sekhon et al., 2017). Participants will be provided with details of the survey in the PIS when they enter the study. Consent to participate in the survey will be taken at the point of entry to the study. Participants will be under no obligation to complete the survey and can participate in the feasibility arm of the study without completing it. The survey will be anonymous and the participant can withdraw up to the point it is completed. Questions will ask about their attitude towards, understanding of and burden of completing the outcome measures. It will be a mix of choice and Likert scale questions with some free text open questions. The survey should take no more than 15 mins to complete. Participants can be supported to complete the survey by an advocate, therapist or member of the research team who can read out the questions and record their responses, but will not influence the answers. The survey will be on paper for ease of completion in the clinical setting.

8. Statistics and Data Analysis

To answer the research questions mainly descriptive statistics will be used and data presented using bar charts and pie charts. The focus group data will be analysed using thematic analysis (Braun and Clarke, 2013).

The percentage of patients who:

- a. are admitted for at least 72 hours and are approached
- b. are approached who agree to participate
- c. agree and can complete the three measures

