To identify trends for vertical perception loss and discharge status narrative statistics will be utilised. For instance the numbers of participants identified as having vertical perception loss who are discharged home will be investigated. If possible a Spearman Rank Correlation with Fisher-Z between outcome measure score and discharge information (e.g. length of stay in days, MRS score or Barthel Score) will be used. These tests have been chosen as the data is ordinal and are expected to be non-

parametric in nature. An ordinal regression will allow identification of which outcome measure is most likely to relate to discharge information.

A Spearman Rank Correlation with Fisher-Z will be completed on each element of the SCP and Catherine Bergego Scale against SVV to identify if any specific elements of the measures are more indicative of vertical perception loss than others. An ordinal regression will allow identification of which elements of the SCP and Catherine Bergego Scale are most likely to relate to SVV tilt.

The percentage of patients able to complete the measures, along with scores and confidence intervals for the outcome measures will be used to determine potential sample size for larger trials (Eldridge et al., 2016) and assess the change in vertical perception loss during in-patient admission.

It is known that neglect (Esposito et al., 2021) and pushing behaviour (Dai et al., 2022) improve over time. Therefore, changes in a sub-sample of the population will be tracked to inform future interventional research. For the subsample who have outcomes taken on discharge a Wilcoxon Sign Rank test will be used to identify the change in scores of the measures during in-patient stay. This will be completed for the whole study population and for each of the subgroups defined as mild, moderate or severe vertical perception loss.

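### Exploratory discharge analyses could cheaply add falls per stroke-unit day and NIHSS-adjusted results beside the planned falls count and unadjusted associations

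*Combined protocol and SAP*

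**What the plan says.** The secondary research question in section 1 asks, for patients able to complete the assessments, "does vertical perception loss show any relationship with" discharge destination, care package size, number of inpatient falls and functional independence. Section 8 opens by saying that "mainly descriptive statistics will be used".

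**Falls.** Section 6 (Study protocol) extracts the number of falls from the notes at discharge from the unit. Section 8 tabulates that number. No rate, offset or per-day summary appears. Time on the unit differs between patients:
- Section 5 requires "Admitted to stroke unit with a length of stay of over 72 hours".
- Section 6 schedules a last assessment attempt at 4 weeks after admission for patients still unable to complete.
- The Trial Summary gives "Length of Participant Involvement: Equal to length of stay on the stroke unit".

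Length of stay is used in two ways: as an overall mean in the descriptive table, and as one of the quantities the scores may be correlated with ("length of stay in days, MRS score or Barthel Score"). It is not used as time at risk.

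**Severity.** Admission NIHSS is collected (section 6) and appears in section 8 only as a median in the descriptive table. The discharge correlations and the regression ("An ordinal regression will allow identification of which outcome measure is most likely to relate to discharge information") name no covariate. Elsewhere the protocol says that "those with significant strokes are more likely to present with vertical perception loss" (section 6, Recruitment), and that people with "neglect or lateropulsion require longer periods of rehabilitation and have a worse functional outcome" (section 1).

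**The concern.** A patient on the unit for four weeks has more days on which to fall than one discharged on day four. If patients with vertical perception loss stay longer, as the background section suggests for neglect and lateropulsion, they can show more falls per patient at the same daily risk.

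Severity raises a similar issue. Asking whether any association exists needs no adjustment. Section 8 goes a step further and wants to identify which of the three measures relates most to discharge information. A measure can lead that comparison because it follows overall stroke severity more closely, and unadjusted results alone would not let a reader see this. What is at stake is how the exploratory results are read when later work on measuring vertical perception is designed. Completion percentages and completion times are not involved.

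**Working it through.** The plan gives no falls rate, correlation, alpha or power, so it has no figure of its own to reproduce. Everything below marked as assumed is illustration.

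**1. Falls and days at risk.** Expected falls = daily rate × days.
- Minimum stay: 72 hours = 3 days (section 5). A patient present for the last attempt: 4 weeks = 28 days (section 6). Ratio for two such individuals at equal daily rate: 28/3 = 9.3.
- Between groups, the ratio of mean counts = ratio of daily rates × ratio of mean stays. Mean stay by loss status is not given. At equal daily rates, equal mean stays give a count ratio of 1, an assumed 10 v 20 days gives 2, and an assumed 7 v 28 days gives 4.

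**2. Correlation induced by severity.** If a score relates to outcome only through NIHSS, the unadjusted correlation is a × b, where a = corr(score, NIHSS) and b = corr(NIHSS, outcome). Assumed a = 0.3 to 0.5 and b = 0.5 to 0.6 give 0.3 × 0.5 = 0.15 up to 0.5 × 0.6 = 0.30.

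**3. Ranking two measures.** Simulation with 20,000 runs and normal variables. Measure A has a = 0.5 and measure B has a = 0.3. A has no direct link to outcome. B has either none, or a coefficient of 0.1 on its severity-independent part. No sample size is planned: 24 and 50 are the pilot sizes cited in section 4, and 100 is a larger case. Entries are the chance that A ranks first.

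| n | No direct link, raw Spearman (b = 0.5 / 0.6) | No direct link, NIHSS-partial | B has direct link, raw (b = 0.6) | B has direct link, NIHSS-partial |
|---|---|---|---|---|
| 24 | 0.635 / 0.663 | about 0.51 | 0.535 | 0.366 |
| 50 | 0.695 / 0.733 | about 0.51 | 0.554 | 0.295 |
| 100 | 0.766 / 0.814 | about 0.51 | 0.578 | 0.218 |

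With b = 0.5 and the direct link, the raw figures are about 0.50 to 0.52. Entering the measures together does not by itself remove the issue. With two standardised predictors in a linear rank regression, the coefficient difference is (r_A − r_B)/(1 − r_AB), where r_A and r_B are the correlations with outcome. Its sign is that of the raw difference, so the order is unchanged.

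**4. What adjustment costs.**
- 95% half-width at zero correlation, raw: tanh(1.96·√(1.06/(n−3))) = 0.414 at n=24 and 0.286 at n=50. Partial, with n−4: 0.423 and 0.289.
- Partial r = (r − ab)/√((1−a²)(1−b²)). For an assumed raw r of 0.45: a=0.3, b=0.5 gives 0.30/0.826 = 0.36; a=0.5, b=0.6 gives 0.15/0.693 = 0.22.
- Ordinal regression on three scores, simulated with a six-category outcome (assumed score–score 0.3, score–NIHSS 0.4, NIHSS–outcome 0.55): adding NIHSS raises the scores' standard errors by about 9% (n=24), 6% (n=50) and 5% (n=100).
- Patients per predictor with four predictors: 24/4 = 6, 50/4 = 12.5, 100/4 = 25.

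**The case against.** The plan can be defended on several grounds, and much of the defence stands.

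- The question is whether loss shows a relationship with outcome, not whether it does so independently of severity. Section 1 gives the purpose as early identification of people who will need more rehabilitation or care. A marker that works partly through severity can still do that. This stands: the unadjusted associations are a legitimate target.
- A reader might infer that severity adjustment is excluded. The documents do not support that. Section 8 lists no covariates at all, so the most one can say is that no severity term is specified.
- A reader might infer that falls will be biased roughly 9-fold, or that a false-positive rate can be attached to them. Neither is supported. The 9.3 compares two individual extremes, mean stay by loss status is unknown, and no formal falls test is written. Falls are not among the examples given for the Spearman correlation. The descriptive table also shows mean stay, so a crude overall rate could be worked out, though not by loss status.
- If loss itself prolongs stay, the extra days are part of how loss leads to falls, and a rate removes that part. This stands, and it is why the rate should accompany the count.
- At the cited pilot sizes neither ranking is dependable: with a small direct link at n=24, the adjusted ranking still favours the wrong measure in 37% of runs. This stands too.
- No stated decision rests on the ranking. Section 8 bases future sample size on completion percentages and scores.

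What survives is narrower. The plan sets out to compare the measures and to relate loss to falls, and it already collects the data that would help a reader interpret both results.

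**Conclusion.** This is a worthwhile, inexpensive improvement to exploratory secondary analyses, not an error in the plan. The stronger conclusion, that the discharge analyses are invalid as written, is not supported: they answer the question posed, and the primary feasibility outcomes are untouched.

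The text does show that falls have no time-at-risk denominator, although stay varies and the protocol expects longer rehabilitation with neglect or lateropulsion. It also shows that the comparison of measures has no specified severity term, although NIHSS is collected and severity is linked to loss. The amount of distortion cannot be derived. The ranking figures rest on assumed correlations, normal variables and severity fully captured by one variable, so they show that the mechanism is plausible at realistic sample sizes and do not predict its size here.

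**What to change.** Amend the wording of section 8, before results are seen, as follows:

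1. Report falls per 1,000 stroke-unit days by loss status beside the count, descriptively, with a note that the rate and the total answer different questions.
2. Show partial Spearman correlations adjusted for admission NIHSS beside the unadjusted ones for the discharge outcomes.
3. Only where numbers allow, show the discharge-outcome ordinal regression with and without NIHSS.
4. Label the unadjusted results as unadjusted associations that remain valid for identifying patients, and state that no ranking of measures is treated as dependable at small n.
5. Do not adjust MRS or Barthel for length of stay, which may be a consequence of loss.

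No new data or patient burden is needed: falls, length of stay and NIHSS are already planned. The statistical price is slightly wider intervals, an adjusted regression that may be unusable at about 24 patients, and possible removal of real effect where severity and loss overlap. That last risk is why both versions should be shown.

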
Identification of vertical perception loss early after stroke may be important in allowing identification of:

- Those who will require longer periods of rehabilitation
- Those who are likely to present with lateropulsion/pushing or neglect
- Those who may require more care and support on discharge

- Those with milder vertical perception loss who may be at risk of falling (Dai et al., 2021a), but do not have neglect or lateropulsion
- Changes in vertical perception over time
- Changes in vertical perception in response to rehabilitation interventions
- Those who will and will not respond to rehabilitation interventions and hence support appropriate allocation of therapy resources.

Currently, the established methods of measuring subjective vertical perception (visual, haptic or postural) are not feasible in the acute stroke environment (Piscicelli and Pérennou, 2017, Perennou et al., 2008). The main reasons are the equipment required being unsuitable in a clinical environment and the burden on the person with stroke. There is evidence that it is possible to use the more basic 'bucket test' to identify those with subjective visual vertical loss in the acute setting (Chang et al., 2019, Zwergal et al., 2009). Participants in these studies had central and peripheral vestibular disorders so is not translatable to the acute stroke population. Furthermore, some people with stroke who present with vertical perception loss present with normal visual vertical but a tilt in postural vertical (Karnath et al., 2000). Therefore, assessment of visual vertical alone may not identify all of those with vertical perception difficulties. As discussed, above vertical perception loss has been related to lateropulsion and neglect. Hence, the measurement of SVV, lateropulsion and neglect, is likely to be required to identify most people with vertical perception loss in the acute stroke setting.

The aim of this research is to establish the feasibility of using this suite of known outcome measures to identify those with vertical perception loss following stroke in the acute setting. If the use of these outcome measures is found to be feasible it will be the basis of further research to design and propose a reliable and valid method for measuring vertical perception loss in an acute stroke setting.

The principal research question that this study will aim to address is:

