will be calculated. Demographic data of the participants will be tabulated for display including: number of patients with left or right stroke, number of patients with haemorrhage or infarct stroke, female/male/non-binary/other gender, mean length of stay, location of stroke, median NIHSS on admission, median MRS and Barthel Index on discharge, place of discharge (home/care home/other), care needs on discharge (nil, one, two, three or four calls per day or 24 hour and number of carers required), number of in-patient falls, median minutes of therapy per day (for OT and Physiotherapy) and median number of days on which OT and Physiotherapy were received.

The main outcome will be the percentage of consenting patients who are able to complete the three outcome measures within four weeks of admission. The percentage of patients able to complete each of the outcome measures individually will be calculated to see if one of the outcome measures is more feasible than the others. Reasons for non-completion will be collated for each of the outcome measures and presented using an appropriate tool. The mean time and standard deviation (SD) to complete all three and each individual outcome measure will be presented. To identify the most feasible time point to complete the outcome measures median (and confidence intervals) time to completion of each outcome measure and time to completion of all three outcome measures will be calculated. The percentage of participants completing each or all of the measures at 48 hours, 1 week, 2 weeks and 4 weeks will be presented.

The median scores and confidence intervals for the SCP and Catherine Bergego scale will be calculated, as well as the mean and SD for the bucket test. The percentage of patients with vertical perception loss will be reported – this will be defined as a positive test on one or more of the measures (SVV >2.5°, Catherine Bergego Scale >1, SCP >0.5). For each patient it will be noted if they test positive on one, two or all three measures. This will assist in informing which of the measures will be required in future studies.

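### The element-level correlations use the visual vertical (SVV) as their only reference but are read as showing which elements indicate vertical perception loss, so SCP elements that pick up postural tilt may be under-ranked

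*Combined protocol and SAP*

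**What the plan says.** The planned element-level analysis in Section 8 has two parts:

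- A Spearman correlation with Fisher-Z of each SCP and Catherine Bergego element "against SVV to identify if any specific elements of the measures are more indicative of vertical perception loss than others".
- An ordinal regression to identify "which elements of the SCP and Catherine Bergego Scale are most likely to relate to SVV tilt".

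Both use SVV from the bucket test and nothing else. The first is interpreted as being about vertical perception loss, the second only as being about SVV tilt.

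The same split appears elsewhere. The secondary research question at the end of Section 1 is narrow: "Is there a trend for any element of the SCP or the Catherine Bergego to be more correlated with SVV tilt". The matching objective in the Trial Summary and in Section 2 is broad and asks about a relationship to vertical perception loss.

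Three other statements bear on the choice of reference:

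- Section 1 reports that "some people with stroke who present with vertical perception loss present with normal visual vertical but a tilt in postural vertical", and concludes that "assessment of visual vertical alone may not identify all of those with vertical perception difficulties".
- The first secondary research question in Section 1 gives the SCP the postural role: "evidence of subjective postural vertical (SPV) tilt on SCP". It groups the Catherine Bergego Scale with the bucket test, as evidence on the visual vertical.
- Section 8 says of vertical perception loss that "this will be defined as a positive test on one or more of the measures", with cut-offs of 2.5° for SVV, 1 for Catherine Bergego and 0.5 for SCP.

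**The concern.** The protocol includes the SCP because SVV is expected to miss some patients. If the SCP elements are then judged only by agreement with SVV, a patient with postural tilt and normal SVV counts against the element that found the tilt, even though Section 8 classes that patient as having loss. The analysis can mark down the information that the SCP was added to supply.

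What is at stake is how the result is read. Section 1 presents the study as the basis for designing a later method of measuring vertical perception loss. A published ranking of elements as more or less indicative of loss could be carried into that work, although the analysis measures only association with SVV.

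**Working it through.** The plan attaches no sample size, expected correlation or error rate to this analysis, so there is no figure to reproduce. The check has two parts.

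**1. Reference against conclusion**

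| Place | Reference or definition | What is concluded |
|---|---|---|
| Section 1, research question on elements | SVV tilt | SVV tilt |
| Section 8, element regression | SVV tilt | SVV tilt |
| Section 8, element correlation | SVV | vertical perception loss |
| Trial Summary and Section 2, objective | none named | vertical perception loss |
| Section 8, definition of loss | any of three measures positive | vertical perception loss |

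The first two rows are coherent. The third is not, because SVV is one of three ways of meeting the definition in the last row.

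**2. Direction of the effect (all inputs assumed)**

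*Hand example.* Take 40 patients: 10 with both tilts, 6 with visual tilt only, *k* with postural tilt only, and 24 − *k* with neither. Element A flags every postural tilt (10 + *k* patients). Element B flags the 10 patients with both tilts and nobody else. Neither has false positives for loss.

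With SVV tilt present in 16 and absent in 24:

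- phi(A, SVV) = [10(24 − *k*) − 6*k*] / √[(10 + *k*)(30 − *k*) × 16 × 24]
- phi(B, SVV) = (10 × 24 − 0 × 6) / √(10 × 30 × 16 × 24) = 240 / 339.4 = 0.71, whatever *k* is
- Share of patients with loss found: A = (10 + *k*)/(16 + *k*); B = 10/(16 + *k*)

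| *k* | phi(A, SVV) | phi(B, SVV) | Loss found by A | Loss found by B |
|---|---|---|---|---|
| 0 | 240/339.4 = 0.71 | 0.71 | 10/16 = 63% | 10/16 = 63% |
| 2 | 208/359.2 = 0.58 | 0.71 | 12/18 = 67% | 10/18 = 56% |
| 4 | 176/373.9 = 0.47 | 0.71 | 14/20 = 70% | 10/20 = 50% |
| 6 | 144/384 = 0.38 | 0.71 | 16/22 = 73% | 10/22 = 45% |

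With no postural-only patients the two elements tie on both criteria. Each added postural-only patient lowers A against SVV while A finds a larger share of those with loss.

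*Simulation with imperfect elements and a continuous SVV.* Each scenario had 200,000 patients, 50% with loss. A share *q* of those with loss had postural tilt only, and a share *c* of those with visual loss also had postural tilt. SVV was normal with mean 6° (SD 2.5°) in visual loss and mean 0° (SD 1.2°) otherwise. The postural element had sensitivity 0.8 and the visual-type element 0.4 or 0.8; both had specificity 0.95. For *c* = 0.6 and visual sensitivity 0.8:

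| *q* | Postural: rho with SVV | Visual: rho with SVV | Postural: phi with any loss | Visual: phi with any loss |
|---|---|---|---|---|
| 0 | 0.42 | 0.64 | 0.50 | 0.76 |
| 0.1 | 0.35 | 0.64 | 0.53 | 0.69 |
| 0.2 | 0.28 | 0.63 | 0.55 | 0.63 |
| 0.3 | 0.22 | 0.62 | 0.58 | 0.56 |
| 0.5 | 0.13 | 0.56 | 0.63 | 0.44 |

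Across the 24 scenarios with *q* > 0 (*q* = 0.1, 0.2, 0.3, 0.5; *c* = 0.3, 0.6, 0.9; two visual sensitivities):

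- in 15 the postural element ranked below the visual one against SVV but above it against any loss;
- in 6 it ranked below on both;
- in 3 it ranked above on both (all with *c* = 0.9 and visual sensitivity 0.4).

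In all six scenarios with *q* = 0 the two references gave the same order.

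**The case against.** The strongest reply is that the analysis answers the question asked. The research question in Section 1 and the regression sentence in Section 8 speak only of SVV tilt, and the analysis is exploratory and secondary in a feasibility study. That stands. It makes this a fault in the stated conclusion, not in the choice of correlation.

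SVV is also hard to replace. The any-measure definition contains the SCP and Catherine Bergego totals, so correlating their elements with it would be circular. No separate measure of the postural vertical is taken. This also stands, and it is why the fix leaves the reference unchanged.

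The plan already records whether each patient is positive on one, two or all three measures. That helps at the level of whole measures, but it does not show which SCP elements score when SVV is normal.

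A reader might infer three stronger things that the documents do not support:

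- *That SCP elements will rank lowest.* Section 1 says visual vertical loss and lateropulsion are related in magnitude, so some correlation with SVV is expected. The order depends on the postural-only share, the overlap of the two tilts and the strength of the other elements, none of which the documents give.
- *That Catherine Bergego elements are affected in the same way.* Section 1 treats that scale as evidence on the visual vertical, so the postural argument reaches only the SCP.
- *That elements will be dropped because of this analysis.* No section says so. Section 8 gives the count of positive measures the task of informing which measures future studies need.

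**Conclusion.** The mismatch is real: the reference is SVV, the conclusion is about vertical perception loss, and the protocol itself says the two differ in some patients. SCP elements that detect postural tilt in SVV-normal patients may be under-ranked.

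The direction rests on the protocol's own statement that such patients exist, and on the SCP detecting their tilt. The size is unknown. The figures above are illustrations with every input assumed. The hand example also reduces the scores to yes or no and leaves out patients positive only on Catherine Bergego, whom Section 8 would count as having loss.

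The primary feasibility outcomes are not touched. The wording should still be put right before the analysis, because it determines what the element ranking can be said to show.

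**What to change.** 1. In the correlation sentence of Section 8, and in the matching objective in the Trial Summary and Section 2, limit the conclusion to association with SVV tilt. This brings them into line with the research question in Section 1 and the regression sentence in Section 8.
2. Add one descriptive table of SCP element scores by SVV status (tilted or normal, at the plan's 2.5° cut-off) in all participants who completed both measures. Catherine Bergego elements may be added. Do not restrict the table to SCP above 0.5: the total is the sum of its elements, so that filter would guarantee that some element scores.
3. State that a low correlation with SVV does not show that an element is uninformative about vertical perception loss.
4. State that postural-only loss cannot be validated in this study, because no independent measure of the postural vertical is taken. The table can describe SVV-normal participants who score on the SCP, but it cannot confirm that they have perceptual loss.

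The cost is a narrower claim and one extra table. No new data and no additional patient or staff burden are involved.
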